## 2.0 STUDY OBJECTIVES

## 2.1 Primary Objectives

2.1.1 To evaluate the response rate (RR) in patients with mRCC after treatment with HD IL-2 immediately following SABR to multiple metastatic sites. RR has been highly correlated (p<0.0001) to overall survival [34]. RECIST 1.1 criteria will be used to measure RR and it will consist of complete response (CR) and partial response (PR).

## 2.2 Secondary Objectives

- **2.2.1** To evaluate the overall survival (OS), which is defined as the time between date of registration and the date of death due to any cause. In analyzing the OS, it is important to take into account the MSKCC prognostic criteria defined by Motzer et. al. mRCC patients and compare the outcome in the appropriate risk categories [90].
- **2.2.2** To evaluate progression free survival (PFS), which is defined as the time between date of registration and the first date of documented disease progression or date of death due to any cause.
- **2.2.3** To evaluate time to progression (TTP), which is defined as time between date of registration and date of documented progression.
- **2.2.4** To evaluate the local control rate of irradiated lesions.
- **2.2.5** To evaluate median response duration, which is defined as the time between the date a response (CR or PR) was first seen until date of progression.
- **2.2.6** To measure treatment-related tumor-specific immune response.
- **2.2.7** To evaluate the tolerability and toxicity of this regiment as measured according to CTCAE v4.0.
- **2.2.8** To measure the improvement in health-related quality of life (HRQoL).

## 2.3 Exploratory Objectives

- **2.3.1** To explore the immunological biomarkers as correlates or predictors for treatment response.
- **2.3.2** To evaluate the cost-effectiveness analysis of this treatment regimen to the other current first and second line treatments for mRCC.

## 2.4 Endpoints

- **2.4.1 Response:** Treatment response will be measured using the immune related RECIST criteria (iRECIST) which are a minor modification of RECIST 1.1 for immunotherapy [91].
- **2.4.2 Death:** Death due to any cause, although in mRCC patient population, the overwhelming majority is expected to be secondary to disease progression.
- **2.4.3 Progression:** Progression will be defined according to the iRECIST criteria and verified by a second set of imaging at least 6 weeks apart.
- **2.4.4 Immune Response:** Immune response will be measured using ELISpot assay, T-cell proliferation assay and ELISA.
- 2.4.5 Toxicity: Toxicity will be measured using CTAE v4.0
- **2.4.6 HRQoL**: HRQoL will be measured using FACT-G, EQ-5D and FKSI questionnaire at baseline, after HD IL-2, and at four-month intervals after treatment.
- 2.4.7 **Cost-effectiveness analysis**: Health care utilization data needed to assess costs will be obtained from treatment records to include costs of hospitalization, treatment, ER visits, physician and clinic visits and medications. Markov modeling with probabilistic sensitivity analysis will be used to correlate quality-adjusted survival and cost.

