#### 4.4 Duration of Follow Up

Subjects will be followed for ten years or death (although findings will be analyzed and reported at a median follow up of 2-4 years), whichever occurs first. Subjects removed from treatment for unacceptable adverse events will be followed until resolution or stabilization of the adverse event. The follow-up will be every 8 weeks (+/- 2 Weeks) from study registration with imaging studies and physical exam every 8 weeks for the first eight months, then every 12 weeks (+/- 2 Weeks) until two years, then every four months thereafter for a total of five years, and then every six months (+/- 1 month) for a total of ten years. See section 5.0 for detail.

Subjects who show progressive disease will be followed for survival and will no longer strictly adhere to study calendar. QOL questionnaires will be completed every 4 months until 1 year after treatment.

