## 6.0 Measurement of Effect

## 6.1 Antitumor Effect

For the primary endpoint, response and progression will be evaluated in this study using the new international criteria proposed by the Response Evaluation Criteria in Solid Tumors (RECIST) Committee [JNCI 92(3):205-216, 2000], which was also used by the two randomized trials of HD IL-2 being used as historic controls for this trial [35, 36]. The only change from RECIST v.1.1 being implemented in this study is a confirmation of new lesions or progressive disease (PD) by a second scan >6wks apart, based on the immune RECIST (irRC) criteria proposed by Wolchok. et. al that is appropriate for immune-related treatment response [91]. This is primarily because immune response often can take longer time as compared to chemotherapy before producing a radiographic response and during this time new lesions may arise which will eventually regress and if it were not for a second confirmation, these patients would be labeled to have failed therapy. In addition, the majority of mRCC responders to HD IL-2 usually produce a durable response (median response duration of 24 months), therefore, this change will not affect the outcome [35]. Additional criteria for bone lesions and clinical endpoints of pathologic fracture and cord compression are added to this study (see Section 6.1.4).

Changes in only the largest diameter (unidimensional measurement) of the tumor lesions are used in the RECIST v1.1 criteria outlined in http://www.recist.com/.

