#### 6.1.4.3 Evaluation of Best Overall Response

The best overall response is the best response recorded from the start of the treatment until disease progression/recurrence (taking as reference for progressive disease the smallest measurements recorded since the treatment started). The subjects best response assignment will depend on the achievement of both measurement and confirmation criteria.

Target Lesions	Non- Target Lesions	New Lesions	Overall Response	Best Response for this Category
-------------------	---------------------------	-------------	---------------------	---------------------------------------

				Also Requires:
CR	CR	No	CR	≥4 wks. confirmation
CR	Non- CR/Non- PD	No	PR	> 4 wks. confirmation
PR	Non-PD	No	PR	
SD	Non-PD	No	SD	documented at least once ≥4 wks. from baseline
PD	Any	Yes or No	PD	
Any	PD*	Yes or No	PD	no prior SD,
Any	Any	Yes	PD	PR or CR
* In exceptional circumstances, unequivocal progression in non-target lesions may be accepted as disease progression.				

Note: Subjects with a global deterioration of health status requiring discontinuation of treatment without objective evidence of disease progression at that time should be reported as "*symptomatic deterioration*". Every effort should be made to document the objective progression even after discontinuation of treatment.

Note: If subjects respond to treatment and are able to have their disease resected, the patient's response will be assessed prior to the surgery.

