# 11.3 Data Analyses Plans

This is a single-arm Phase II trial of SABR and HD IL-2 for mRCC patients. PFS and OS, will be estimated using the Kaplan-Meier approach along with the 95% confidence interval. Exact binomial method will be used to calculate the response rate, toxicity and the corresponding 95% confidence interval. One-sample log-rank test [121] will be used to test if the survival endpoints such as OS or PFS are significantly different from those in the historical control reported in McDermott et. al [35].

Generalized estimating equation (GEE) analysis will be conducted to test if the median number of spots in Elispot of the PBMC collected from patients are significantly different over time (before starting of treatment and after SBRT, at 8 weeks and six months). T-Cell proliferation SI will also be evaluated in the same manner.

HRQol, CEA and quality adjusted survival time analysis is described in Section 10.

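### First-scan progression that is never verified has no scoring rule for PFS, so the historical PFS comparison may be biased toward the regimen; TTP has no rule for death

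*Combined protocol and SAP*

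**What the plan says.** Section 2.4.3 defines the progression endpoint: "Progression will be defined according to the iRECIST criteria and verified by a second set of imaging at least 6 weeks apart". Section 6.1 repeats the requirement as "confirmation of new lesions or progressive disease (PD) by a second scan >6wks apart" and presents it as the trial's only change from RECIST v1.1. It adds that "this change will not affect the outcome", arguing from the durability of responses. The same section says that RECIST was the standard in the two randomized HD IL-2 trials used as historical controls.

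Section 2.2.2 ends PFS at "the first date of documented disease progression or date of death due to any cause", and section 6.1.7 likewise counts progression or death. Section 2.2.3 defines TTP as the "time between date of registration and date of documented progression" and does not mention death.

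On follow-up, section 4.4 states: "Subjects who show progressive disease will be followed for survival and will no longer strictly adhere to study calendar". Section 4.1.1 allows the reserved untreated site to be irradiated once PD is met.

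Section 11.3 plans Kaplan-Meier estimates and states: "One-sample log-rank test [121] will be used to test if the survival endpoints such as OS or PFS are significantly different" from one of those HD IL-2 trials. It gives no event or censoring rules, no significance level and no reference curve.

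**The concern.** A first PD scan can lack a verifying scan because the patient starts another treatment, withdraws or misses imaging. For such a patient 2.4.3 and 2.2.2 can give different answers. Under 2.4.3 there is no progression; under 2.2.2 the first scan can be taken as the documented date. Nothing else in the plan decides between them.

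If 2.4.3 governs, the patient's PFS runs on to death or is censored. Either way, events that a single-scan rule would count are delayed or lost. Section 6.1 indicates that the historical trial was assessed without the verification step, so the observed and reference curves would then use different event definitions. The one-sample test could favour the regimen with no treatment effect. Section 1.4 says the secondary outcomes, PFS among them, could be used to justify a phase III trial.

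The argument in 6.1 that verification changes nothing concerns responders. Patients who never respond supply most early PFS events, and it does not cover them.

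**Working it through.** **The passages side by side.**
- 2.4.3 and 6.1: PD needs a second scan, at least or more than 6 weeks later.
- 6.1.4.1: the 6-week wording follows new lesions; whether it also covers the 20% increase is unclear.
- 6.1.4.2: new lesions or unequivocal non-target progression are PD, with no second scan stated.
- 6.1.4.4.1: a new bone lesion needs a repeat bone scan.
- 6.1.4.5 and 6.1.4.6: fracture away from a treated site, and cord or cauda equina compression, count once a radiologist confirms them.
- No section scores PD that lacks its verifying scan.

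**The plan's own figures.** There is no sample size, power or expected median for PFS or TTP to reproduce. The response-rate design in 11.2 (3/17, 9/33) does reproduce: early stopping probability 0.427, expected N 26.2, type I error 0.197, power 0.805. None of these depends on how PFS is scored.

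**Inputs to an illustration.** From the plan: 33 patients and 8-week imaging (8/4.345 = 1.84 months). Assumed: exponential time to first PD with median 4 months; exponential survival after PD with median 12 months; a probability q of leaving before the second scan; follow-up of 24 to 48 months; verified PD dated at the first scan; every PD subject to verification; no true benefit; two-sided 0.05.

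**Share unverified.** Death within 8 weeks of PD: 1 − 2^(−1.84/12) = 0.10. Adding leavers: 1 − 0.90 × (1 − q) = 0.19, 0.33 (0.325 before rounding) and 0.55 for q = 0.10, 0.25 and 0.50.

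**Test.** Z = (O − E)/√E, where O is observed events and E is expected events under the true first-PD hazard ln 2/4 per month. A false-favourable result is Z < −1.96.

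| Scoring | q | PD unverified | Median PFS (months) | 12-month PFS | False-favourable |
|---|---|---|---|---|---|
| First scan | any | – | 4.0 | 13% | about 2% |
| Carried to death | 0 | 10% | 4.1 | – | about 2% |
| Carried to death | 10% | 19% | 4.7 | 18% | 29% |
| Carried to death | 25% | 33% | 5.8 | 27% | 79% |
| Carried to death | 50% | 55% | 9.0 | 41% | 99% |
| Leavers censored at first PD | 10% | 19% | – | – | 7% |
| Leavers censored at first PD | 25% | 33% | – | – | 25% |
| Leavers censored at first PD | 50% | 55% | – | – | 76% |

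In the censored rows, deaths within the 8 weeks still count as events.

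**Sensitivity.** With a 6-month median, carrying to death gives about 16%, 57% and 96%. A separate run fixed deaths before the second scan at 10% and other unverified PD at 20%, with medians of 3, 6 and 9 months and one-sided 0.025. The false-favourable rates were 0.82, 0.46 and 0.26 carried to death; 0.21, 0.21 and 0.20 censored; and 0.021, 0.020 and 0.017 with first-scan scoring.

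**The case against.** The case against a broader claim is strong, and most of it stands.

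- A reader might infer that patients who die before verification are unscored. For PFS they are not: death from any cause is an event in 2.2.2 and 6.1.7. In the q = 0 row deaths alone move the median by 0.1 month and leave the error rate at about 2%. The gap for death is confined to TTP.
- A reader might infer that no progression counts without a second scan. Sections 6.1.4.2, 6.1.4.5 and 6.1.4.6 let some count at once. The simulation sends every PD through verification, so it overstates the effect to that extent.
- Symptomatic deterioration might look like another unverified-PD group. Section 6.1.4.3 defines it as "Subjects with a global deterioration of health status requiring discontinuation of treatment without objective evidence of disease progression at that time", so there is no first PD scan to verify, and it asks for every effort to document progression later.
- Section 4.4 may mean verified PD when it relaxes the calendar. It does not say. If it does, that section does not itself cause verifying scans to be missed.
- Section 2.2.2 can be read as first-scan scoring, and then there is almost no bias.
- Section 11.3 names OS and PFS for the historical test, so nothing supports a claim that TTP is overstated against a historical curve.

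What remains is that 2.4.3 and 6.1 state the verification rule generally, the sections disagree, and no text settles the case of a missing second scan when PFS goes into the historical test.

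**Conclusion.** The point holds as an unresolved scoring rule with possible upward bias in PFS. A reader might conclude that PFS is overstated. The documents do not establish that, because it depends on which reading the analyst adopts and on how many patients leave before the second scan, and the documents give no such share.

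If 2.4.3 is applied as written, the illustrated false-favourable rate runs from 7% (censored, 10% leaving) to 99% (carried to death, 50% leaving), against about 2% with first-scan scoring. Those figures rest on the assumed 4-month median, 12-month survival after PD and two-sided 0.05. The direction, toward the regimen, is the same in every scenario with leavers. TTP separately lacks a rule for death.

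PFS and TTP are secondary endpoints. The phase III decision in 11.2 rests on response rate and is unaffected. This should be corrected, but it does not undermine the primary design.

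**What to change.** - **2.4.3 and 6.1.7:** state that PD with no evaluable verifying scan at least 6 weeks later is scored on the date of the first PD assessment, whatever the reason the scan is missing, and that only a later scan showing no PD cancels it.
- **11.3:** use PFS to first documented PD for the comparison with the historical trial, and report confirmed-PD PFS as a secondary analysis.
- **2.2.3 and 11.3:** report TTP as cumulative incidence, with death without progression as a competing event.
- **2.4.3, 6.1, 6.1.4.1 and 6.1.4.2:** reconcile which kinds of progression need verification.

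The cost is wording only; no new data are needed. PFS may look somewhat shorter than under the verification rule.

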## 3.0 Subject ELIGIBILITY

Subjects must meet all of the inclusion and exclusion criteria to be registered to the study. Study treatment may not begin until a subject is registered.

## 3.1 Inclusion Criteria

- 3.1.1 Pathologic evidence of clear cell RCC
- 3.1.2 Radiographic evidence of metastatic disease. CT and Bone Scan must be performed with 21 days (+ 7 days) of registration. MRI of brain can be performed within 6 months prior to registration.

3.1.2.1 Patients with any number of metastatic site are allowed to enroll. However, only up to six sites will be selected for SBRT treatment, at the discretion of the treating radiation oncologist.

- 3.1.3 Patient must have >1 lesion. Combined diameter of the lesions must be of size >1.5cm.
- 3.1.4 Previous treatment with surgery, radiation, chemotherapy, immunotherapy or any targeted agents are allowed provided that:

3.1.4.1 Chemotherapy was administered > 28 days before the start of HD IL-2 3.1.4.2 Surgery, radiation, immunotherapy or any targeted agents was administered > 14 days before the start of HD IL-2

- 3.1.5 Age  $\geq$  18 years.
- 3.1.6 Performance status ECOG 0, 1.
- 3.1.7 Patient must be eligible for HD IL-2 treatment
- 3.1.8 Patient must be eligible for SABR to one or more extra cranial sites.
- 3.1.9 Adequate organ and marrow function as defined below:
  - leukocytes ≥ 3,000/mcL
  - absolute neutrophil count ≥ 1,500/mcL
  - platelets ≥ 50,000/mcl
  - total bilirubin
- ≤ 2mg/dL
- AST(SGOT)/ALT(SPGT) ≤ 2.5 X institutional upper limit of normal
- 3.1.10 Women of child-bearing potential and men must agree to use adequate contraception (hormonal or barrier method of birth control; abstinence) prior to study entry, for the duration of study participation. Should a woman become pregnant or suspect she is pregnant while participating in this study, she should inform her treating physician immediately.
  - 3.1.10.1 A female of child-bearing potential is any woman (regardless of sexual orientation, having undergone a tubal ligation, or remaining celibate by choice) who meets the following criteria:
    - Has not undergone a hysterectomy or bilateral oophorectomy; or
    - Has not been naturally postmenopausal for at least 12 consecutive months (i.e., has had menses at any time in the preceding 12 consecutive months).
- 3.1.11 Ability to understand and the willingness to sign a written informed consent
- 3.1.12 Adequate Renal function with  $Cr \le 1.6 \text{ mg/dL}$ .
- 3.1.13 Adequate cardiac function (adequate perfusion; no ischemia) on thallium (or Tc) stress test
- 3.1.14 Adequate pulmonary function on PFT (FEV1 >65%; DLCO>60%).

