The SABR prescription dose will be delivered to the periphery of the planning target volume (PTV, see below for definitions). Investigators will have discretion in choosing from either of the biologically equivalent dose levels using one or three fractions, although a single fraction is preferred over three fraction treatments. Treating physician will have further discretion in selecting the number and location of sites to treat if >6 sites of disease are present. Maximum number of lesions treated is deemed as feasible per the treating radiation oncologist. Physician's will be **REQUIRED** to leave at least one site of disease for the purpose of measuring a radiographic response (see section 6.1) at a non-treated site, as this is part of the primary endpoint. If left untreated, this site can be treated once patient meets the definition of progressive disease (PD) (see section 6). To clarify the definition of "site", each site is an area or organ with active extracranial disease (</=3 in the liver = one site and </=3 in the lung= one site) identified by CT scan, or PET/CT, within 4 weeks prior to initiation of SBRT (up to 2 contiguous vertebral metastasis will be considered a single site of disease). For example: a patient with 4 right axillary lymph nodes, L1-L2 bone metastasis, 3 right lung lesions, 1 left lung lesion, 2 liver lesions, and T2-T3 bone metastasis would be defined as having 6 sites of disease. Preference should be given to the largest feasible disease site, symptomatic sites and sites where palliative and preventative (i.e. to prevent a pathologic fracture in weight bearing bone, impending cord compression, impending SVC compression etc.) indications are applicable. The gross target/tumor volume (GTV) should be at least 2cm^3 in size, corresponding to roughly a 1.5 cm diameter tumor. This is to ensure that adequate tumor volume and therefore adequate tumor cells (roughly 10^8 -10^9 cells/cm^3 [96]) are killed for antigen presentation. Treating physicians should choose their dose based on established planning guidelines at their center including their ability to respect normal tissue tolerance listed below. It is not required that all targets be treated with the same dose fractionation. A dose from the following table should be used:

	Total Cumulative Dose Encompassing 95% of Planning					
	Target Volume (Gy)					
Number of	Protocol Compliant Minor Deviation * MinorDeviation					
Fractions						

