#### 6.1.2 Disease Parameters

Measurable disease. Measurable lesions are defined as those that can be accurately measured in at least one dimension (longest diameter to be recorded) as  $\geq$ 10 mm with spiral (Helical) CT scan. All tumor measurements must be recorded in millimeters (or decimal fractions of centimeters).

Non-measurable disease. All other lesions (or sites of disease), including small lesions (longest diameter <20 mm with conventional techniques or <10 mm using spiral CT scan), are considered non-measurable disease. Bone lesions, leptomeningeal disease (patients excluded), ascites, pleural/pericardial effusions, lymphangitis cutis/pulmonis, inflammatory breast disease, abdominal masses (not followed by CT or MRI), and cystic lesions are all non-measurable.

Target lesions. All measurable lesions up to a maximum of 3 lesions per organ and 6 lesions in total, representative of all involved organs, should be identified as **target lesions** and recorded and measured at baseline. Target lesions should be selected on the basis of their size (lesions with the longest diameter) and their suitability for accurate repeated measurements (either by imaging techniques or clinically). A sum of the longest diameter (LD) for all target lesions will be calculated and reported as the baseline sum LD. The baseline sum LD will be used as reference by which to characterize the objective tumor response.

Note: Lesions receiving SABR will be called "treated lesion" which should not be confused with "target lesions" defined here for the for the purpose of radiographic measurement. Treated lesions and target lesions are mutually exclusive lesions. Therefore, treated lesions will not be used as target lesions for evaluating response. Since patients with ANY number of metastasis is eligible for this study, in the instance where patient has only one or few site of disease and all of them are treated, appearance of new lesions (either measurable or non-measureable) will constitute PD.

Non-target lesions. All other lesions (or sites of disease) including any measurable lesions over and above the 6 target lesions should be identified as **non-target lesions** and should also be recorded at baseline. Measurements of these lesions are not required, but the presence or absence of each should be noted throughout follow-up.

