#### 6.1.4 Response Criteria

#### 6.1.4.1 Evaluation of Target Lesions

Complete Response (CR): Disappearance of all target lesions, determined by two separate observations conducted not less than 4 weeks apart. There can be no appearance of new lesions.

Partial Response (PR): At least a 30% decrease in the sum of the longest diameter (LD) of target lesions, taking as reference the baseline sum LD. There can be no appearance of new lesions.

Progressive Disease (PD): At least a 20% increase in the sum of the LD of target lesions, taking as reference the smallest sum LD recorded since the treatment started, or the appearance of one or more new lesions verified by a second scan > 6 weeks apart.

Stable Disease (SD): Neither sufficient shrinkage to qualify for PR nor sufficient increase to qualify for PD, taking as reference the smallest sum LD since the treatment started.

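### A CR or PR on the primary endpoint needs a measurable, unirradiated target lesion, but the plan does not ensure one, conflicts on treating all sites, and has no counting rule.

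*Combined protocol and SAP*

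**What the plan says.** - **Entry.** 3.1.3: "Patient must have >1 lesion. Combined diameter of the lesions must be of size >1.5cm". No single lesion has to be measurable, and 3.1.2.1 admits any number of metastatic sites.
- **What can be a target lesion.** 6.1.2 sets 10 mm on spiral CT as the threshold for measurable disease. Its list of non-measurable disease begins "Bone lesions, leptomeningeal disease (patients excluded), ascites". It also bars irradiated lesions: "Treated lesions and target lesions are mutually exclusive lesions".
- **How response is scored.** 6.1.4.1 defines PR as "At least a 30% decrease in the sum of the longest diameter (LD) of target lesions" relative to baseline, and CR as disappearance of all target lesions. In 6.1.4.3, "The subjects best response assignment will depend on the achievement of both measurement and confirmation criteria". The table's three CR or PR rows pair a target-lesion CR or PR with a non-target result.
- **Untreated site.** 4.1.1 requires physicians "to leave at least one site of disease for the purpose of measuring a radiographic response". It refers to section 6.1 and ties this site to the primary endpoint.
- **All sites treated.** 6.1.2 provides for a case "in the instance where patient has only one or few site of disease and all of them are treated", and there says only that "appearance of new lesions (either measurable or non-measureable) will constitute PD". Section 5.1.15.2, on the post-treatment biopsy, also foresees that every lesion may have been treated.
- **Evaluability.** 6.1.1 asks for SABR, one HD IL-2 course and re-evaluation at 8 and 16 weeks. It does not ask for a target lesion.
- **Decision rule.** 11.2 stops at 3 or fewer responses in 17 and calls the regimen promising at more than 9 in 33.

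**The concern.** A patient can satisfy the wording of entry, treatment and evaluability and still have no lesion from which the table can produce a CR or PR. Such a patient can reach progression on the written criteria but cannot be a responder. The situation is not far-fetched: 4.1.1 steers SABR towards the largest feasible site, so the lesions most likely to be measurable are those most likely to be removed from the target set.

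The go decision turns on 10 versus 9 responses in 33, so the handling of one or two such patients can settle it. With no rule written down, that handling would be chosen after the scans have been seen. The conflict between 4.1.1 and 6.1.2 makes matters worse, because the text gives two answers on whether an unirradiated response site must exist at all.

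**Working it through.** **1. The plan's own design.** Inputs from 11.2: p0 = 0.23, p1 = 0.368, stop if X1 ≤ 3 of 17, go if total ≥ 10 of 33.

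P(go | p) = Σ over x = 4 to 17 of P(X1 = x) × P(X2 ≥ 10 − x), with X1 ~ Bin(17, p) and X2 ~ Bin(16, p).

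- p = 0.23: early stopping 0.427, average N = 17 + (1 − 0.427) × 16 = 26.2, type I error 0.197.
- p = 0.368: power 0.805.

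These match the stated 0.43 and 26.2 and respect the 0.20/0.20 limits. The sample-size calculation is not in dispute.

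**2. Does the text guarantee a target lesion?** Two constructed cases:

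| Case | 3.1.3 (>1 lesion, >15 mm combined) | Untreated site left (4.1.1 wording) | Possible target lesion (6.1.2) |
|---|---|---|---|
| 20 mm adrenal mass irradiated, 6 mm lung nodule left | 20 + 6 = 26 mm: met | yes | none: 6 mm < 10 mm, and the mass is treated |
| 20 mm soft-tissue lesion irradiated, bone lesion left | met | yes | none: bone is non-measurable, and the other lesion is treated |

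A 20 mm sphere has volume π/6 × 2³ = 4.2 cm³, above the 2 cm³ guidance for irradiated lesions in 4.1.1. If both patients complete treatment and the two re-evaluations, they meet 6.1.1. Neither has a target-lesion sum, so no CR or PR row applies.

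**3. The three passages on treating all sites.** 4.1.1 makes one untreated site mandatory. 6.1.2 and 5.1.15.2 describe patients with none. These cannot all govern the same patient.

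**4. Size if such patients are counted as non-responders.** The documents give no frequency, so m = 1, 2, 3 of 33 is an assumption. They respond at rate 0 and the others at p, so the average rate is p(33 − m)/33, entered in the formula of step 1.

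| m | Average rate, p = 0.368 | Power | Average rate, p = 0.23 | Type I error |
|---|---|---|---|---|
| 0 | 0.368 | 0.805 | 0.230 | 0.197 |
| 1 | 0.357 | 0.768 | 0.223 | 0.171 |
| 2 | 0.346 | 0.727 | 0.216 | 0.147 |
| 3 | 0.335 | 0.682 | 0.209 | 0.125 |

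Placing exactly m such patients at random across the two stages gives nearly the same values: power 0.770, 0.731, 0.688 and type I error 0.170, 0.145, 0.122.

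**5. Size if they are not evaluable and are replaced.** Power stays at 0.805 for 33 assessable patients. Enrolment becomes 33/(1 − u), rounded up, where u is the share without a target lesion. For assumed u of 5%, 10% and 20% this is 35, 37 and 42.

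**The case against.** **4.1.1 already implies measurability.** It gives the purpose of the untreated site and points to section 6.1, where measurability is defined. Read that way, a 6 mm nodule does not serve the rule. This stands as evidence of intent, and it narrows the gap. But the wording can be met by a site that cannot be measured, and it cannot help patients covered by the all-treated provision in 6.1.2.

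**Such patients might simply not be evaluable.** 6.1.1 says evaluable subjects are classified by the definitions that follow, so someone who cannot be classified might be left out and replaced. There is then no power loss, only extra enrolment. This reading is open, but it is not written: the replacement rule in 5.5.3 covers patients who did not receive a cycle of HD IL-2, not patients without a target lesion. The power figures therefore describe one of two readings.

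**The magnitude is assumed.** It is. The number of such patients is unknown. The power loss also takes 36.8% as the rate among patients with a target lesion, whereas 11.2 states it for treated mRCC patients generally.

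**A stronger inference to resist.** A reader might infer that the bone criteria inflate the false-positive rate: 6.1.3 uses bone scan for overall response when positive at baseline, and 6.1.4.4.2 lets a radiologist call a PR on uptake with no threshold. The documents do not support that. Under 6.1.2 bone is non-measurable and so falls among the non-target lesions. On the 6.1.4.3 table, a bone-scan PR has no row that yields an overall PR without a target-lesion response. What is missing is a sentence saying so.

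**Conclusion.** The point holds as a gap in the primary-endpoint definition together with a contradiction in the text. Following the plan as written can admit patients who cannot score a response, and the plan does not say how they enter the 17 and 33. The contradiction between 4.1.1 on one side and 6.1.2 and 5.1.15.2 on the other is firm and needs no assumption.

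The size is illustrative. If such patients count as non-responders, one is enough to take power below the stated 80% (about 0.77), and three take it to about 0.68. If they are replaced, power is unaffected and the cost is enrolment. A reader might conclude that the trial is underpowered as designed. That does not follow, because the design reproduces and the documents do not show how many such patients there are.

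**What to change.** - **(a) Reconcile 4.1.1, 5.1.15.2 and 6.1.2** on whether all sites may be treated. That clinical choice belongs to the authors. If all-sites treatment remains possible, they must say how the primary endpoint is scored for those patients.
- **(b) Require a baseline target lesion for the primary endpoint.** At least one lesion that is measurable and eligible as a target lesion under 6.1.2, as reconciled, should be recorded before SABR. If an untreated site is kept as the response site, 4.1.1 should say that it must be measurable under 6.1.2.
- **(c) Fix the counting rule in 6.1.1 and 11.2** before responses are scored: state how any patient without a target lesion counts in the 17 and 33. Counting them as non-responders is conservative (type I error about 0.17, 0.15 or 0.12 for 1, 2 or 3 patients) at the power cost shown above. Exclusion with replacement keeps power but raises enrolment.
- **(d) Complete 6.1.4.3.** State that bone-scan response enters through the non-target column, and that neither a bone-scan PR alone nor response of irradiated lesions alone makes an overall CR or PR.

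The cost is wording, using baseline scans that the plan already requires, plus slightly narrower eligibility under (b). For patients already enrolled, the entry requirement in (b) comes too late, but (c) and (d) can still be applied.
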